the screening visit from a parent/guardian, and assent will be obtained from youth by the PI or designated associate investigators. All participants will be informed of their right to withdraw from the study. The purpose of the project, all testing procedures, and study components, and possible risks and inconveniences will be described in detail in language understandable to the parent(s)/guardian(s). The investigator will also explain the study to the minor who is of a younger age and level of understanding. Sufficient time and opportunity will be given for discussion of the research as well as to answer any questions they may have, taking care to minimize or eliminate the perception of coercion or undue influence. When the NIH informed consent and assent forms are signed, parents or guardians will be given a signed copy of the consent and assent form for their records. In the unlikely event that the parents/guardians of protocol-eligible subjects cannot travel to the NIH Clinical Center for a considerable period of time, the PI or other protocol staff designated to obtain consent will obtain informed consent by a telephone conversation. Consent may be obtained via telephone and/or another electronic process, rather than in person. In such cases, the written signed consent will be faxed and/or mailed and made part of the patients' NIH records. No research procedures will commence until the investigator has confirmed that written, legally effective consent has been obtained. In general, Investigators obtaining consent (whether in person or over the telephone) will be encouraged to have a second person (who is not obtaining informed consent) present during the entire informed consent discussion and, if applicable, the signature process. Investigators will also document the consent process in a note placed in the research record for all consent discussions.

As noted above, given the minimal risk of the study, the consent of one parent will be considered sufficient for protocol participation except in cases where two signatures are required (for instance because of shared medical decision-making explicated in a divorce decree).

c. Non-English–Speaking Participants

If a child who speaks English has a parent who is found not to be English-speaking is eligible for enrollment, the parent will be provided with the CC Short Written Consent Form for Non-English Speaking Research Participants and a verbal explanation of the

purpose, procedures and risks of the study as described in MAS Policy M77-2, NIH HRPP SOP 12 and 45 CFR 46.117(b)(2). The IRB-approved English consent form will serve as basis for the verbal explanation of the study. All NIH policies on utilizing the “short form” consent process, including having a witness during the "short form" consent process, will be followed.

d. Consent documents

The submitted consent form contains all required elements for consent. One consent form, for parents/guardians to sign for their minor children, and one assent form, for minor children, are submitted with this protocol. See **Appendices C & D**.

14. Data and Safety Monitoring

a. Data and safety monitor

For this un-blinded, minimal risk trial, we propose that the PI will be sufficient to monitor the study.

b. Data and safety monitoring plan for Non-IND

The following monitoring plan will be implemented to ensure the protocol data are in compliance with Good Clinical Practice (GCP), NICHD Institutional Review Board (IRB) and Federal regulations. This will ensure the validity, accuracy and integrity of the data.

1. Study Staff Responsibilities

[name], Principal Investigator, will be responsible for all aspects of the study. Some responsibilities may be delegated to other associate investigators as detailed in the *Study Personnel Sheet & Delegation of Responsibility Log*.

2. Source Documentation and Case Report Forms

[name], PhD is responsible for coordinating data collection and will review the data for accuracy and completeness within seven days of each subject visit.

The PI along with study associate investigators will conduct the monitoring. Patient consent documents, primary outcome and safety laboratory results, and diagnostic test results will be monitored for accuracy, correct dating, and agreement between case report forms and source documents. As case report forms are entered electronically into the NICHD Clinical Trials Database, the computer system contains logs indicating changes made and the circumstances leading to these changes.

The medical records of active subjects (defined as subjects undergoing study procedures in the current year) will be monitored quarterly or more frequently as required. Any major findings will be summarized in writing and reported to the NICHD Institutional Review Board, if indicated. Investigator credentials, training records, and the delegation of responsibility log will also be reviewed on an annual basis.

3. IRB and DSMC Documentation

All IRB documentation can be found in iRIS. The Principal Investigator, *[name], PHD*, is responsible for maintaining IRB correspondence related to this protocol, including records of all reviews of the study and submissions to the IRB. This protocol does not meet the criteria as outlined in the NIH HRPP SOP 17 for data to be submitted to a data safety monitoring committee. The PI and IRB can provide adequate oversight for this open trial.

Clinical Trial Studies (non IND/IDE) will have random audits performed by the NICHD Office of the Clinical Director:

<https://science.nichd.nih.gov/confluence/display/ocd/Protocol+Navigation>).

4. FDA Documentation

Not Applicable – no IND.

5. Study Completion

Upon completion of the study *[name], PhD* will retain possession of the electronic Protocol Binder in a secure location. HHS regulations require that subjects' records be maintained for at least three years after completion of a study. Since subjects of this investigation include children age 7-11.9 years, even longer record retention is required. All records will be retained until all participants have reached age 23 years.

6. Data safety and monitoring board (DSMB)

Because there is no blinded component to these studies, the studies do not involve administration of any pharmaceutical agents, and the procedures are of minimal risk, we propose

that a formal DSMB is not required, and that the investigators and IRB can adequately supervise this study. All adverse events will be documented and reported to the NICHD IRB as described above in ‘Protocol Monitoring Plan.’ We expect that the risk for an adverse event will be within the “Rare but serious (Event Rate < 1%)” category.

15. Quality Assurance

a. Quality assurance monitor

[name], PhD is responsible for coordinating data collection and will review the data for accuracy and completeness within seven days of each subject visit. The NICHD Standard Operating Procedure for Intramural Clinical Protocol Monitoring (rev. 5.20.2015) will be followed.

b. Quality assurance plan

Quality assurance will be executed in accordance with the NICHD quality assurance plan. Adverse events and protocol deviations will be reviewed and recorded on a weekly basis at the SGO protocols review meeting.

Protocol-specific monitoring will include:

- Review of biochemical results from OGTT testing within 72 hours of test.
- Daily data retrieval from continuous glucose monitoring devices.
- Weekly data retrieval from continuous actigraph and heart rate monitoring devices.
- Weekly data retrieval from the NIH Toolbox Assessment center for cognitive measure outcomes.

16. Reporting of Unanticipated Problems, Adverse Events and Protocol Deviations

Event Characterization and Reporting to the IRB and Clinical Director (CD):
Unanticipated problems, non-compliance, and other reportable events will be reported to the NIH IRB as per Policy 801 (“Reporting Research Events.”). All reportable events occurring during

the study, including those observed by or reported to the research team, will be recorded. Reportable Events will be reported by the PI verbally and in writing as soon as possible, but not more than 7 days after the PI first learns of the event. Deaths will be reported to the Clinical Director within 24 hours after the PI first learns of the event. All adverse events (serious and non-serious, expected and unexpected) will be reported annually to the IRB for review. Electronic data sheets or summary language will be supplied for IRB review of adverse event reports at continuing reviews.

The Principal Investigator is responsible for detecting, documenting, and reporting unanticipated problems, adverse events (AEs), including serious adverse events (SAEs), and deviations in accordance with NIH policy, IRB requirements, and federal regulations.

17. Alternatives to Participation

The current proposal is a physiological study that does not treat any known condition; as a result, there are no alternatives other than non-participation. Participants and their families will be informed that they will not receive treatment as a result of study participation. For participants found to have medical conditions, treatment referrals will be provided.

18. Privacy

All research activities will be conducted in as private a setting as possible. This will be most noteworthy during the history and physical examination will be conducted in a private room in the pediatric day hospital.

19. Confidentiality

- Samples and data will be stored using codes that we assign. Data will be kept in password-protected computers and on the secured data server hosted by the Section on Growth and Obesity as described above. Samples will be kept in locked storage. Only study investigators will have access to the samples and data.
- De-identified results will be posted on clinicaltrials.gov

20. Conflict of Interest

a. Distribution of NIH guidelines

- NIH guidelines on conflict of interest have been distributed to all investigators.

b. Conflict of interest

This is a covered protocol because of the research agreement with Cogstate LTD.

There are no conflicts-of-interest to report for NIH investigators. Non-NIH investigators will abide by the conflict-of-interest policies of their own institutions.

c. Role of a commercial company or sponsor

Cogstate supplies software for collection of cognitive data during the study and will have access to some data under the terms of the signed agreement. The company had no role in the study design and will have no role in the decision to publish.

21. Technology Transfer

There is a technical transfer agreement negotiated with Cogstate LTD. See Collaborating Researchers and Affiliated Institutions under Management of Data and Samples above.

22. Research and Travel Compensation

Volunteers will be compensated for time and research-related inconveniences as follows:

1. Complete screening visit: \$100
2. Complete outpatient test visits days #1-5: \$100/visit (5 visits; \$500 total)
3. Complete final testing visit, day #6: \$150
4. Complete CGM wear: \$20/wear (6 days; \$120 total)
5. Complete wrist activity monitor wear: \$10/day (6 days; \$60 total)

(Study total \$930)

Volunteers taking part in the MRS Supplemental arm of the study will be compensated for time and research-related inconveniences as follows:

1. Complete baseline MRS scan: \$100
2. Complete follow up scan #1 (immediately before testing session): \$75
3. Complete follow up scan #2 (immediately after testing session): \$75

(Study Total \$250)

Compensation will be prorated for parts completed if subjects do not complete the study as guided by the reimbursement plan above.

No additional incentives will be provided.

Payment will be provided in the name of child in check form.

Payment will be issues within 7 days after completion of last study visit.
Travel/lodging compensation. Local travel may be covered to facilitate the daily visits required.

- No escort fee will be provided.
- NIH employees or staff who wish to have their child participate during work hours must have permission from their supervisor. NIH employees or staff must either participate outside of work hours or take leave in order to receive compensation.

23. References

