data described above was not dependent on adiposity.^{48, 64, 65} Also, the non-metabolic parameters such as cognitive function are independent of weight. Therefore, our proposed intervention will likely affect healthy weight and overweight children equally within these outcomes. Finally, our intervention is designed to be a preventative strategy intended to prevent dysfunctional metabolism before the onset of pathology such as Impaired Glucose Tolerance or Diabetes Mellitus Type 2 and be feasible for broad spread application into the community setting where the majority of subjects are expected to be healthy. For broad spread application, it is pivotal that preliminary data demonstrate potential benefits and negligible adverse outcomes in all subject populations within which it will be applied. Given this, we will study healthy weight and overweight children who do not have evidence of metabolic disease.

Magnetic Resonance Spectroscopy Arm: Use in Exercise Physiology

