In final summary, there are few data for the effects of experimentally interrupting sedentary behaviors on metabolism, cognition, mood, or dietary intake, and no such data for programs that study such interruptions in a sustained fashion. However, what are available suggest that one-session interventions with at least moderate intensity bouts applied 2 or 3 times per hour may be successful at improving glucose homeostasis by decreasing circulating insulin. Therefore, we plan to conduct a pilot study that examines sustained metabolic outcomes from interrupting daily sedentary behavior in children applied with 3-minute interrupting bouts every 30 minutes for a 3-hour duration over 6 days. With this study we will also collect exploratory mechanistic data from liver and muscle spectroscopy. Our chosen intervention mirrors our one-session preliminary trials and is in line with similar published intervention trials.^{64, 65} We have chosen the details of this strategy to maintain the potential of translation to the real-world setting. Although some preliminary data have been obtained with an intervention applied every 20 minutes⁶⁴ instead of every 30 minutes, this intervention is too frequent to be practical in a school setting. Additionally, the duration of 6 days has been chosen as an ideal intermediary to demonstrate sustained effects prior to broad spread application that will require extensive resources and as of yet are not strongly data-supported. Finally, in addition to glucose homeostasis, we will explore the potential impacts of interrupting prolonged sitting on children's executive function, mood, anxiety, dietary intake, and usual physical activity habits which aim to strengthen the rationale for broad application of this approach in the school setting.

2. Study Objectives

Project Goal: The overall goal of this research is to examine whether providing brief interruptions in prolonged sitting produces long-term salutary changes in metabolism, without adversely impacting executive function, attention, anxiety, mood, or dietary intake. As a bridge between the acute studies that have demonstrated efficacy for this approach and long-term

school- or home- based translational programs, we will examine if brief interruptions of sedentary behavior applied for 6 consecutive days will produce sustained improvements in metabolism and to explore any changes in cognitive function or energy intake in children with intervention.

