Objective 1: To investigate if daily interruptions of sedentary behavior (sitting) versus prolonged sitting on 6 consecutive days improve glucose homeostasis. **Hypothesis 1a:** Compared to non-interrupted sedentary behavior, interrupted behavior will result in significantly lower insulin and glucose incremental area under the curve (iAUC) during a 3-hour oral glucose tolerance test.

Hypothesis 1b: As measured by continuous glucose monitoring, children with daily interrupted sitting will have lower average 24-hr glucose iAUC and lower mean amplitude glycemic excursion (MAGE) than children who engage in non-interrupted sedentary behavior.

Objective 2: To investigate if daily interruption of sedentary behavior adversely influences cognitive and psychological measures, dietary intake, or usual physical activity. **Hypothesis 2:** Executive function, attention, mood, anxiety, dietary intake, and physical activity (at times outside the testing period) will not differ significantly between children randomized to daily interrupted versus daily non-interrupted sedentary behavior.

Objective 3: To investigate if acute or daily interruption of sedentary behavior affects intramyocellular lipid content within the vastus lateralis, tibialis anterior or soleus muscles.

Hypothesis 3a: Acute interrupted sedentary behavior will decrease intramyocellular lipid content. **Hypothesis 3b:** Daily interrupted sedentary behavior will increase resting/basal intramyocellular lipid content.

3. Subjects

a. Description of study populations

The proposed intervention has demonstrated acute efficacy in the general pediatric population, among both healthy weight⁶⁵ and overweight children, ages 7-12 years. Therefore, we will enroll generally healthy child volunteers in a 1:1 ratio of healthy and overweight. We will adhere to a maximum accrual ceiling of 150 participants. Based on previous experience, we anticipate that no more than 20% of screened children will be

ineligible for the study. Thus, we will randomize up to 120 participants and, anticipating that at most 36 children will drop-out of the study before completion or have technical issues limiting data analysis, we expect at least 84 participants to complete the protocol (our target completion sample size is based on power analyses described below).

Withdrawals/dropouts will not be replaced.

i. Inclusion criteria

Participants will qualify for the study if they meet the following criteria:

- (a) Good general health.

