- b. **Secondary outcomes** are glucose iAUC obtained during the oral glucose tolerance test; mean iAUC as obtained from 24hr- continuous glucose monitoring, and Mean Amplitude Glycemic Excursion (MAGE) as obtained from 24hr- continuous glucose monitoring. Tertiary outcomes are cognitive function (working memory, inhibition, attention, and processing speed), mood, anxiety, daily physical activity (steps counts/day), and dietary intake at the final test meal. Improved circulating glucose values as demonstrated by lower glucose iAUC would directly support our primary insulin outcome and would be clinically relevant as this result would indicate improved metabolism. Additionally, MAGE has been demonstrated to be associated with metabolic control such that elevated MAGE is associated with worsening cardiometabolic outcomes in individuals with diabetes.¹⁶⁷

The executive function, mood and anxiety outcomes are being collected for independent objectives. This group of measures is an important objective to provide information that will be necessary to know for feasibility of this intervention. This intervention is poised to community application such as school class rooms. Therefore, it is important to understand if executive function is adversely affected by the intervention as this would limit its feasibility for implementation. Finally, all analyses will be performed within the subgroups of healthy weight and overweight subjects to evaluate for differential effectiveness based on weight status.

10. Statistical Analysis

- a. Analysis of data.** Prior to conducting the main model analysis, descriptive analyses will be conducted on all outcome and covariate to assess potential outliers and calculate summary statistics. If significant deviations from the assumed distribution (e.g.: normal) occur, then appropriate transformations will be applied to fulfill model assumptions. If transformations are not sufficient to meet model assumptions, then nonparametric tests will be used. Descriptive statistics will investigate correlations between variables at pre-test and post-test to assess potential confounders prior to analyses.

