The parallel study design allows for the examination of between-individual comparisons of test effects and within-individual longitudinal test effects (i.e. repeated daily CGM metrics). Significance level will be set at $\alpha = 0.05$. Covariates will include: age, sex, race/ethnicity, baseline cognitive ability (for cognitive outcomes only), baseline homeostatic model of insulin resistance (HOMA-IR), body fat mass (except for subgroup analysis by weight status), and Tanner stage. We will also evaluate for a weight status interaction (intervention x healthy weight / overweight).

The following analyses will be performed:

- i.** Participant characteristics will be summarized using means (standard deviations) and frequencies.
- ii.** Baseline (time 0) values for participant characteristics, insulin, glucose, heart rate, and blood pressure between the groups will be compared using t-tests.
- iii.** The primary analysis will be ANCOVA comparing children randomized to the two groups for insulin iAUC at the end-study oral glucose tolerance test, with age, sex, race/ethnicity, HOMA-IR, body fat mass, and Tanner stage as variables in the model. If all covariates are nonsignificant, unpaired t-tests will be reported for the differences in OGTT insulin iAUC by condition (prolonged vs interrupted sitting). Similar analyses will be used to examine glucose iAUC, 5- or 6-day average 24hr CGM iAUC and 24hr MAGE. (Subjects may only have 5 days of CGM data if a device is

accidentally removed and replaced at the next visit or subject uses a medication that interacts with glucose readings such as acetaminophen-after which 24hrs of data will be omitted from analysis). Mixed models will also be used to assess the influence of prolonged vs. interrupted sitting on insulin and glucose iAUC over the 3 hours of observation. To evaluate differences in the dependent variables at each time point, planned comparisons of model-based mean differences between each time points will be calculated. Additionally, mixed models will be used to assess condition influence on mean 24hr CGM glucose iAUC and 24hr MAGE.

- iv. ANCOVA or (as indicated above) t-tests will investigate differences in working memory, inhibition, attention, processing speed, mood, anxiety, and kcal intake between prolonged sitting and interrupted sitting at the post- test.

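### Hypothesis 2 answers a question about harm with a non-significant difference; model 10.a.v may adjust for activity and sleep measured after randomisation, and the 10.a.iv ANCOVA names no mood or anxiety baseline

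*Combined protocol and SAP*

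**What the plan says.** **The question asked.** The project goal in Section 2 is metabolic benefit "without adversely impacting executive function, attention, anxiety, mood, or dietary intake". Objective 2 is: "To investigate if daily interruption of sedentary behavior adversely influences cognitive and psychological measures, dietary intake, or usual physical activity". The Subject Selection text in Section 1 gives the reason for studying both weight groups: "it is pivotal that preliminary data demonstrate potential benefits and negligible adverse outcomes in all subject populations within which it will be applied". Section 9.b adds that "it is important to understand if executive function is adversely affected by the intervention as this would limit its feasibility for implementation".

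**The criterion.** Hypothesis 2 states that the outcomes "will not differ significantly between children randomized to daily interrupted versus daily non-interrupted sedentary behavior". Section 10.a sets alpha at 0.05. No margin, confidence-interval rule or power is given for these outcomes.

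**The analyses.**
- 10.a.iv compares the arms at post-test, by ANCOVA or t-test, on cognition, mood, anxiety and energy intake.
- The only outcome-specific baseline in the 10.a covariate list is "baseline cognitive ability (for cognitive outcomes only".
- 10.a.v uses mixed models for pre-post scores of cognition, mood and anxiety, controlled for significant covariates. The candidates include free-living activity and sleep.
- 10.a.vi repeats every analysis within each weight group.
- Section 10.a also says: "Descriptive statistics will investigate correlations between variables at pre-test and post-test to assess potential confounders prior to analyses".

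**The timing.** Under 4.d, randomisation covers all test visits. Under 4.d.i.f, the wrist accelerometer is worn from day 1 to day 6 for free-living activity and sleep efficiency, and its data are to show whether activity outside the sessions changes because of the intervention. Under 4.d.ii, PANAS-C and STAIC are given on day 1 at time 0. Steps per day is a tertiary outcome in 9.b, but Section 10 names no analysis of it.

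**The concern.** There are three related weaknesses.

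1. **Criterion.** A non-significant difference does not show that harm is negligible. Under a criterion of no significant difference, fewer completers and noisier data make the favourable reading easier to reach. Sections 1 and 9.b intend these results to inform use in schools, so the reading matters.
2. **Covariates.** Free-living activity may be changed by the intervention. If it is changed and also affects cognition or mood, adjusting for it removes that part of the effect. If some unmeasured factor drives both activity and the outcome, adjusting can create a difference. The plan lets one variable be both a possible effect and a candidate adjuster.
3. **Baselines.** Mood and anxiety are measured before the first session, but the post-test ANCOVA does not name those scores. They could enter only through the correlation screen or through model 10.a.v.

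**Working it through.** **The plan's own figures.** There is no power figure for Hypothesis 2. Section 10.b gives 21 evaluable per group for a metabolic effect of d = 0.8 at 80% power: 21 × 2 arms × 2 weight groups = 84, and 120 − 36 = 84. The figure of 21 reproduces as a one-sided t-test at 0.05; a two-sided test needs 26. Sidedness is not stated, and this point does not depend on it.

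**Inputs.**
- Per arm, assuming 1:1 allocation: 42 (84 completers), 21 (one weight group), 60 (all 120 complete).
- r = .66 to .82, the PANAS-C retest range in 4.c.x; applying it to STAIC and Cogstate is an assumption.
- Cogstate SD 10 (4.c.ix).
- Harms of 0.5 SD (5 Cogstate points) and 0.3 SD (3 points) are illustrative.
- Two-sided 0.05 (assumed).

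**Formula.** The miss rate is the chance that a noncentral t with noncentrality d / (s·√(2/n)) falls inside the critical values. In SD units:
- post-test alone: s² = 1, df = 2n − 2
- pre-post change: s² = 2(1 − r) = .68 to .36, df = 2n − 2
- ANCOVA with own baseline: s² = 1 − r² = .564 to .328, df = 2n − 3

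Example at n = 42, where √(2/42) = 0.218, with r = .66. The noncentrality for 0.5 SD is 0.5/0.218 = 2.29 for post-test alone, 0.5/(0.825 × 0.218) = 2.78 for change, and 0.5/(0.751 × 0.218) = 3.05 for ANCOVA.

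**Chance that a 0.5 SD harm is missed:**

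| Per arm | Post-test alone | Pre-post change | ANCOVA with baseline |
|---|---|---|---|
| 42 | 38% | 22% to 4% | 15% to 2% |
| 21 | 65% | 52% to 25% | 44% to 21% |
| 60 | 22% | 9% to 0.5% | 5% to 0.3% |

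The post-test column assumes that the other covariates explain no variance. If they explained 30% (assumption), 38% would fall to 23% and 65% to 53%.

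**Cognition.** The plan already gives cognition a baseline, so the last column applies: a 5-point loss is missed 15% to 2% of the time at 42 per arm. A 3-point loss is missed 56% to 34%.

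**Gain from the mood and anxiety baseline.** Against post-test alone the variance cut is r² = 44% to 67%. Against the change score the variance ratio is (1 − r²)/[2(1 − r)] = (1 + r)/2 = .83 to .91, a cut of 17% to 9%.

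**Adjusting for activity.** The part removed from the estimate is (arm effect on activity) × (within-arm slope of the outcome on activity). The documents give neither. With assumed values of 0.3 to 0.6 SD and 0.2 to 0.4 SD per SD, the product runs from 0.3 × 0.2 = 0.06 to 0.6 × 0.4 = 0.24 SD. This shows the mechanism; it does not estimate the bias.

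**The case against.** The strongest reply is that this is a pilot, the outcomes are tertiary, and Hypothesis 2 is a prediction. **This largely stands.** A reader might infer that the plan will declare no harm from a non-significant test. No passage says so; the wording only leaves that reading open. Nor do the documents require a margin for every tertiary outcome, which would turn exploration into a set of non-inferiority tests.

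A reader might also infer that mood and anxiety baselines go unused. **That is not supported.** Section 10.a.v works with pre-post scores, and 10.a screens pre- and post-test correlations. The 38% and 65% figures therefore describe 10.a.iv alone, and the fairer gain from the baseline covariate is 17% to 9% of variance. What remains is that the documents do not say which model decides Hypothesis 2. Test-meal intake is measured only on day 6, so it has no baseline to add.

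On the covariates, activity and sleep are only to be considered, and only in 10.a.v. A reader might infer that the estimate will be biased. **The text supports possible bias only**, and its direction and size are unknown.

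Finally, 84 is a floor. The 36 expected losses include technical problems that need not affect questionnaires, so the true miss rates may lie nearer the 60-per-arm row.

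**Conclusion.** The point holds as a wording and covariate-timing weakness in the tertiary analyses. The plan has no stated basis for concluding absence of harm, may adjust for a variable it also treats as an effect, and omits collected baselines from one of its two mood and anxiety models. The practical gap is small harms and weight-group results. In the pooled sample a 5-point cognitive loss would usually be detected. A 0.5 SD harm to mood or anxiety would be missed 22% to 4% of the time if 10.a.v uses change scores, but 52% to 25% within a weight group at the completer floor. These sizes rest on the PANAS-C retest range carried over to the other scales, equal arms and illustrative harms. A reader might extend the point to the insulin result; the documents do not support that, because the primary analysis uses neither these criteria nor these covariates.

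**What to change.** (a) In 10.a.v, limit activity and sleep covariates to measures that precede the intervention. For activity, use the screening IPAQ, already a stratification factor. No sleep measure is listed at screening; the day-1 item covering the previous 24 hours is the nearest, since it looks back before the first session. Add free-living steps/day outside the sessions to 10.a.iv as an outcome.

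(b) In 10.a.iv, add the day-1 time-0 PANAS-C and STAIC scores as covariates for mood and anxiety. They follow randomisation but precede the first session. The trial is un-blinded, so state whether the child knows the allocation by then. If so, repeat the analysis with the screening practice scores as a sensitivity check, noting that these may be up to 90 days older.

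(c) Reword Hypothesis 2 along these lines: *Each outcome will be reported as an adjusted difference between arms with its 95% CI. A non-significant difference will not be read as absence of harm.* A margin fixed before analysis is optional, needed only for an outcome on which the sponsor wants to claim no harm.

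**Cost.** Protocol and SAP wording only, with no new data. Some tertiary results, especially test-meal intake and the weight groups, will read as inconclusive. For scale, with a baseline covariate and no true effect, the 95% CI would exclude a 0.5 SD harm 85% to 98% of the time at 42 per arm, but 56% to 79% at 21 per arm.
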